## **ECG evaluations**

All ECG data will be listed by treatment, subject and visit/time, abnormalities will be flagged. Summary statistics will be provided by treatment and visit/time.

## **Clinical laboratory evaluations**

All laboratory data will be listed by treatment, subject, and visit/time and if normal ranges are available abnormalities will be flagged. Summary statistics will be provided by treatment and visit/time.

## **Adverse events**

All information obtained on adverse events will be displayed by treatment and subject.

The number and percentage of subjects with adverse events will be tabulated by body system and preferred term with a breakdown by treatment. An adverse event starting in one period and continuing into the next period is counted only in the onset period. A subject with multiple adverse events within a body system is only counted once towards the total of this body system.

### **11.5.3 Pharmacokinetics**

SOM230 plasma concentration data will be listed by treatment, subject, and visit/sampling time point.

Corporate Confidential Information

### **11.5.4 Pharmacokinetic / pharmacodynamic interactions**

The relationship between reconstructed individual PK profiles and/or the derived PK parameters with various efficacy/PD variables will be explored as appropriate.

Corporate Confidential Information

## **11.6 Sample size calculation**

Data from 23 subjects in each cohort will provide approximately 80% power to detect a drug effect (headache response rate at 30 minutes) that is both clinically significant (defined as the estimated treatment difference  $\geq 30\%$ ) and statistically significant (defined as  $\geq 90\%$  probability of a  $>0\%$  net drug effect) if the true placebo adjusted drug effect is 42%. The power calculation was performed using simulations assuming a correlation of 0.25 and the headache response rate for placebo treatment and 0.9 mg or 1.5 mg SOM230 dose is 30% and 72%, respectively. To account for a potential 20% drop-out rate approximately 30 patients will be enrolled in a cohort.

## **11.7 Power for analysis of key exploratory variables**

Data from 23 subjects will provide 86% power to detect a mean difference of 0.5 headache attack a day using a 1-sided paired t-test at the 0.05 significance level assuming an SD of 0.84 ([Leone et al 2000](#)) and a correlation of 0.5.

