### 4.1 Inclusion criteria

1. Subject is male or female age 18-65 inclusive.
2. Written informed consent must be obtained before any assessment is performed.
3. Subjects must have established diagnosis of episodic cluster headaches (CH) or chronic CH, averaging 2-6 headache attacks per day each lasting at least 45 minutes without treatment, not to exceed 6 attacks per day within the last year.
4. Able to communicate well with the investigator, to understand and comply with the requirements of the study, as well as accepting NOT to share any study information through social media during their participation in the study.
5. Subject is able to self-inject medication subcutaneously or have the assistance of a helper on an out-patient basis, if subject is not domiciled in a clinic for the study.

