### **11.5 Analysis of secondary and exploratory variables**

#### **11.5.1 Efficacy / Pharmacodynamics**

Pain free data will be analyzed using the same approach described for the primary variable.

A generalized linear model with CH type and dose as fixed effects and subject as a random effect will be used to compare the number of headache attacks following SOM230 treatment to baseline assuming the underlying data distribution is Poisson. Over dispersion, if any, will be accounted for as appropriate.

Corporate Confidential Information

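### The 86% power for attack frequency rests on an SD of 0.84 that does not fit the planned Poisson model at 2 to 6 attacks per day

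*Protocol*

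**What the plan says.** Protocol 11.7 gives the power for attack frequency: "Data from 23 subjects will provide 86% power to detect a mean difference of 0.5 headache attack a day using a 1-sided paired t-test", at a one-sided 0.05 level, "assuming an SD of 0.84" "and a correlation of 0.5". The SD is taken from a published verapamil prophylaxis trial.

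Protocol 11.5.1 plans a different analysis of this variable: a generalized linear model with CH type and dose as fixed effects and subject as a random effect, comparing counts after SOM230 with baseline under a Poisson distribution. On dispersion it says only: "Over dispersion, if any, will be accounted for as appropriate".

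Protocol 4.1 admits patients "averaging 2-6 headache attacks per day". The footnotes to Table 8-1 limit baseline diary information to the 3 days before the baseline visit and place the end-of-study visit 3 days after the Period 2 dose. The visible text does not define the period over which attacks after SOM230 are counted.

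**The concern.** For a Poisson count the mean fixes the variance. Once the attack rate and the counting window are set, the SD of the before-after difference can no longer be chosen freely. Section 11.7 takes its SD from outside, and 11.5.1 assumes a distribution that, at the eligible rates, implies a larger one.

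The study is meant to inform whether development continues, 11.7 calls this a key exploratory variable, and Protocol 3.2 expects fewer attacks per day after dosing. If attack frequency shows no clear change, a reader who relies on 86% power may take that as fair evidence against an effect of 0.5 per day. Under the planned model the evidence would be weaker.

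**Working it through.** **Inputs.** n = 23, effect d = 0.5 attacks/day, one-sided alpha 0.05, SD 0.84, correlation 0.5 (11.7). Baseline rate L = 2 to 6 per day (4.1). Baseline window 3 days (stated, Table 8-1 footnote). Post-dose window 3 days (assumed from the end-of-study timing). Dispersion 1 (assumed; pure Poisson).

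**Step 1: the plan's own figure.** SD of the difference = 0.84 × √(2 × (1 − 0.5)) = 0.84. Noncentrality = 0.5/0.84 × √23 = 2.855 with 22 df. One-sided power is 86.9%, so the stated 86% reproduces.

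**Step 2: the SD that the Poisson model implies.** The subject effect cancels in the within-subject contrast. The variance of the difference in daily rates is L/3 + (L − 0.5)/3 = (2L − 0.5)/3. Power = Φ(0.5/√(variance/23) − 1.645). The last two columns give a paired t-test at the same SD, and the dispersion that would bring the SD back to 0.84, which is 0.7056/variance.

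| L per day | Variance | SD | Poisson power | Paired t, same SD | Dispersion for SD 0.84 |
|---|---|---|---|---|---|
| 2 | 1.167 | 1.08 | 71.7% | 69.4% | 0.60 |
| 3 | 1.833 | 1.35 | 55.0% | 52.8% | 0.38 |
| 4 | 2.500 | 1.58 | 44.9% | 43.1% | 0.28 |
| 6 | 3.833 | 1.96 | 33.7% | 32.4% | 0.18 |

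A Wald test on the log rate ratio gives 71.5% at 2/day and 33.7% at 6/day. Simulation (50,000 trials per scenario, with and without between-subject variation in rate) gives about 72%, 45% and 34% at 2, 4 and 6/day.

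**Step 3: what causes the drop.** At the same SD, the t-test and the Poisson model differ by 1 to 2 points. The fall from 86% therefore comes from the SD.

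**Step 4: when 0.84 would fit.** With dispersion 1 and 3-day windows, (2L − 0.5)/3 = 0.7056 gives L = (2.1168 + 0.5)/2 = 1.31 per day, below the eligibility minimum of 2.

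**Step 5: sensitivity over 2 to 6 per day.**
- 3-day baseline, 1-day post-dose: about 21% to 45% (log scale).
- Dispersion 1.5: about 26% to 57%.
- Dispersion 0.5, correctly modelled: about 54% to 93%.
- 7-day windows, which the visible schedule does not support: 59% to 96%.

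**Step 6: if the counts really are as regular as 0.84 implies.** The true SE is 0.84/√23 = 0.175. With the Poisson scale fixed at 1, the model's SE is 0.225, 0.330 and 0.408 at 2, 4 and 6/day. Power = Φ((0.5 − 1.645 × model SE)/0.175), which is about 77%, 40% and 16%.

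**The case against.** Several points on the other side are sound.

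- **The arithmetic in 11.7 is correct and its test is disclosed.** Powering an exploratory count with a simpler test is ordinary practice. A reader might infer that 86% is a miscalculation, or that the t-test causes the shortfall; Steps 1 and 3 rule out both.
- **The post-dose window is inferred.** The assessment grid and parts of the exploratory text are withheld, so a definition may exist there. For the same reason, the absence of an attack-count analysis from the visible SAP does not show that one was omitted.
- **Pure Poisson is a working assumption.** Protocol 1.1 describes attacks as metronomic, which makes under-dispersion plausible. A dispersion of 0.60 at 2/day is conceivable; 0.18 at 6/day is extreme. The source of the SD is not available here, so its window and attack rate cannot be checked.
- **The low end depends on a fixed absolute effect.** A change of 0.5 per day is 25% at 2/day but about 8% at 6/day. With a constant 25% reduction, power would be 72%, 93% and 99% at 2, 4 and 6/day. But 11.7 states an absolute difference, and its power claim has to be judged on that.
- **Step 6 needs the scale fixed at 1.** The dispersion sentence in 11.5.1 names no method, and an estimated scale parameter would also absorb under-dispersion.

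These points limit how firmly 34% to 72% can be stated. They do not reconcile an SD of 0.84 with Poisson counts at the eligible rates.

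**Conclusion.** The concern holds as an inconsistency between a power assumption and the planned model. Under Poisson variation (dispersion 1), with windows of at most 3 days and an effect of 0.5 per day, no rate from 2 to 6 per day reaches 86%; the highest value is about 72%. The range of 34% to 72% is conditional on 3-day windows on both sides, dispersion 1, a one-sided 5% test and n = 23. It should not be read as the trial's actual power: a shorter post-dose window or over-dispersion lowers it, and correctly modelled under-dispersion raises it.

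A reader might also infer that the trial is under-sized. The documents do not support that. Protocol 11.6 sizes each cohort on headache response at 30 minutes, the study is non-confirmatory, attack frequency is exploratory, and no visible decision rule uses it. The point is minor.

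**What to change.** 1. Restate Protocol 11.7 for the model in 11.5.1, giving the counting window before and after dosing, the attack rate and the dispersion assumed. If 34% to 72% is quoted, label it as conditional on 3-day windows and dispersion 1.
2. In 11.5.1, specify an estimated scale parameter or robust standard errors, so that under-dispersion is handled as well as over-dispersion.
3. If the paired t-test is kept as the basis for 86%, justify an SD of 0.84 for patients with 2 to 6 attacks per day. Naming the test alone does not resolve the inconsistency, because the SD drives the result.

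The cost is protocol and SAP wording and a less favourable stated figure for one exploratory variable. Enrolment and conduct do not change.

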## **12      Ethical considerations**

### **12.1    Regulatory and ethical compliance**

This clinical study was designed and shall be implemented and reported in accordance with the ICH Harmonized Tripartite Guidelines for Good Clinical Practice, with applicable local regulations (including European Directive 2001/20/EC, US Code of Federal Regulations Title 21, and Japanese Ministry of Health, Labor, and Welfare), and with the ethical principles laid down in the Declaration of Helsinki.

### **12.2    Responsibilities of the investigator and IRB/IEC**

Before initiating a trial, the investigator/institution should obtain approval/favorable opinion from the Institutional Review Board/Independent Ethics Committee (IRB/IEC) for the trial protocol, written informed consent form, consent form updates, subject recruitment procedures (e.g. advertisements) and any other written information to be provided to subjects. Prior to study start, the investigator is required to sign a protocol signature page confirming his/her agreement to conduct the study in accordance with these documents and all of the instructions and procedures found in this protocol and to give access to all relevant data and records to Novartis monitors, auditors, Novartis Quality Assurance representatives, designated agents of Novartis, IRBs/IECs, and regulatory authorities as required. If an inspection of the clinical site is requested by a regulatory authority, the investigator must inform Novartis immediately that this request has been made.

For multi-center trials, a Coordinating Investigator will be selected by Novartis around the time of Last Patient Last Visit to be a reviewer and signatory for the clinical study report.

### **12.3    Publication of study protocol and results**

Novartis assures that the key design elements of this protocol will be posted in a publicly accessible database such as clinicaltrials.gov. In addition, upon study completion and finalization of the study report the results of this trial will be either submitted for publication and/or posted in a publicly accessible database of clinical trial results.

## 13 Protocol adherence

This protocol defines the study objectives, the study procedures and the data to be collected on study participants. Additional assessments required to ensure safety of subjects should be administered as deemed necessary on a case by case basis. Under no circumstances should an investigator collect additional data or conduct any additional procedures for any research related purpose involving any investigational drugs.

Investigators must apply due diligence to avoid protocol deviations. If the investigator feels a protocol deviation would improve the conduct of the study this must be considered a protocol amendment, and unless such an amendment is agreed upon by Novartis and approved by the IRB/IEC/REB it cannot be implemented. All significant protocol deviations will be recorded and reported in the CSR.

### 13.1 Protocol Amendments

Any change or addition to the protocol can only be made in a written protocol amendment that must be approved by Novartis, Health Authorities where required, and the IRB/IEC prior to implementation.

Only amendments that are intended to eliminate an apparent immediate hazard to subjects may be implemented, provided the Health Authorities and the reviewing IRB/IEC are subsequently notified by protocol amendment.

Notwithstanding the need for approval of formal protocol amendments, the investigator is expected to take any immediate action required for the safety of any subject included in this study, even if this action represents a deviation from the protocol. In such cases, the CTL should be informed and (serious) adverse event reporting requirements ([Section 9](#)) followed as appropriate.

## **15 Appendix 1 Blinding levels**

Not applicable, being a subject only blinded.

## 16 Appendix 2 Liver Safety Monitoring

**Table 16-1 Liver Event and Laboratory Trigger Definitions**

Definition/ threshold	
Liver laboratory triggers	3 x ULN < ALT / AST £ 5 x ULN 1.5 x ULN < TBL £ 2 x ULN
Liver events	ALT or AST > 5 x ULN ALP > 2 x ULN (in the absence of known bone pathology) TBL > 2 x ULN (in the absence of known Gilbert syndrome) ALT or AST > 3 x ULN and INR > 1.5 Potential Hy's Law cases (defined as ALT or AST > 3 x ULN and TBL > 2 x ULN [mainly conjugated fraction] without notable increase in ALP to > 2 x ULN) Any clinical event of jaundice (or equivalent term) ALT or AST > 3 x ULN accompanied by (general) malaise, fatigue, abdominal pain, nausea, or vomiting, or rash with eosinophilia Any adverse event potentially indicative of a liver toxicity *

**Table 16-2 Follow Up Requirements for Liver Events and Laboratory Triggers**

Criteria	Actions required	Follow-up monitoring
Potential Hy's Law case a	Discontinue the study drug immediately Hospitalize, if clinically appropriate Establish causality Complete liver CRF	ALT, AST, TBL, Alb, PT/INR, ALP and yGT until resolution c (frequency at investigator discretion)
ALT or AST > 8 x ULN	Discontinue the study drug immediately Hospitalize if clinically appropriate Establish causality Complete liver CRF	ALT, AST, TBL, Alb, PT/INR, ALP and yGT until resolution c (frequency at investigator discretion)
> 3 x ULN and INR > 1.5	Discontinue the study drug immediately Hospitalize, if clinically appropriate Establish causality Complete liver CRF	ALT, AST, TBL, Alb, PT/INR, ALP and yGT until resolution c (frequency at investigator discretion)
> 5 to £ 8 x ULN	Repeat LFT within 48 hours If elevation persists, continue follow-up monitoring If elevation persists for more than 2 weeks , discontinue the study drug Establish causality Complete liver CRF	ALT, AST, TBL, Alb, PT/INR, ALP and yGT until resolution c (frequency at investigator discretion)

Criteria	Actions required	Follow-up monitoring
> 3 × ULN accompanied by symptoms b	Discontinue the study drug immediately Hospitalize if clinically appropriate Establish causality Complete liver CRF	ALT, AST, TBL, Alb, PT/INR, ALP and γGT until resolution c (frequency at investigator discretion)
> 3 to ≤ 5 × ULN (patient is asymptomatic)	Repeat LFT within the next week If elevation is confirmed, initiate close observation of the patient	Investigator discretion Monitor LFT within 1 to 4 weeks
ALP (isolated)		
> 2 × ULN (in the absence of known bone pathology)	Repeat LFT within 48 hours If elevation persists, establish causality Complete liver CRF	Investigator discretion Monitor LFT within 1 to 4 weeks or at next visit
TBL (isolated)		
> 2 × ULN (in the absence of known Gilbert syndrome)	Repeat LFT within 48 hours If elevation persists, discontinue the study drug immediately Hospitalize if clinically appropriate Establish causality Complete liver CRF	ALT, AST, TBL, Alb, PT/INR, ALP and γGT until resolution c (frequency at investigator discretion) Test for hemolysis (e.g. reticulocytes, haptoglobin, unconjugated [indirect] bilirubin)
> 1.5 to ≤ 2 × ULN (patient is asymptomatic)	Repeat LFT within the next week If elevation is confirmed, initiate close observation of the patient	Investigator discretion Monitor LFT within 1 to 4 weeks or at next visit
Jaundice	Discontinue the study drug immediately Hospitalize the patient Establish causality Complete liver CRF	ALT, AST, TBL, Alb, PT/INR, ALP and γGT until resolution c (frequency at investigator discretion)
Any AE potentially indicative of a liver toxicity*	Consider study drug interruption or discontinuation Hospitalization if clinically appropriate Establish causality Complete liver CRF	Investigator discretion

\*These events cover the following: hepatic failure, fibrosis and cirrhosis, and other liver damage-related conditions; the non-infectious hepatitis; the benign, malignant and unspecified liver neoplasms

aElevated ALT/AST > 3 × ULN and TBL > 2 × ULN but without notable increase in ALP to > 2 × ULN

b(General) malaise, fatigue, abdominal pain, nausea, or vomiting, or rash with eosinophilia

cResolution is defined as an outcome of one of the followings: (1) return to baseline values, (2) stable values at three subsequent monitoring visits at least 2 weeks apart, (3) remain at elevated level after a maximum of 6 months, (4) liver transplantation, and (5) death.

## 1 Introduction

### 1.1 Scope of document

The RAP documents contain detailed information to aid the production of Statistics & Programming input into the Clinical Study Report (CSR) for trial “**CSOM230Y2201**”.

The Statistical analysis plan (SAP) describes the implementation of the statistical analysis planned in the protocol.

### 1.2 Study reference documentation

This SAP has been developed using Clinical Trial Protocol version v04 (incorporating Amendment 04) dated 14 March 2018.

### 1.3 Study objectives

#### 1.3.1 Primary objective

The primary objective of this study is to assess headache response of single subcutaneous (s.c.) dose of SOM230 compared to placebo in managing cluster headache (CH) attack at 30 minutes post-dosing.

#### 1.3.2 Secondary objectives

The secondary objectives of this study are:

- To assess pain free response of single s.c. dose of SOM230 compared to placebo in managing CH attack at 30 minutes post-dosing
- To assess the safety and tolerability of SOM230

Corporate Confidential Information

### 1.4 Study design and treatment

This non-confirmatory study will be conducted in 2 cohorts using a one-sequence two-period design to compare SOM230 vs. Placebo. Following observed efficacy and safety signals in Cohort 1 with the 1.5 mg dose, Cohort 2 of the study assessing efficacy of a lower SOM230 dose (0.9 mg) may be considered.

[figure not shown]
Two consecutive attacks will be treated: first attack will be treated with placebo (Period 1) and the following attack will be treated with SOM230 (Period 2). Approximately 30 subjects will be enrolled in Cohort 1 to receive Placebo s.c. single dose in Period 1 then SOM230 1.5 mg s.c., a single dose in Period 2. Each study cohort will consist of a 21 day screening period, a baseline

period of 3 days prior to the baseline visit, a treatment period (Period 1) lasting up to 3 days then a treatment period 2 of up to 3 days, followed by an end of study visit 3 days after study drug administration in Period 2. The subjects will have up to 5 visits. Similarly, in Cohort 2, approximately 30 subjects will receive placebo s.c. single dose in Period 1 and SOM230 0.9 mg s.c. as a single dose in Period 2.

Each subject will be instructed to self-administer (or to be assisted by a helper, or health care provider) the study medications at the beginning of the CH attack (as early as possible; within 10 minutes of start of attack when pain is at least moderate). In case the subject experiences CH attacks prior to administering study treatment in Period 1 they can use 100% O2 or their conventional treatment to manage their acute attacks experienced before Period 1. If the subject does not have a headache attack in 72 hours post-baseline, or 72 hours post Period 1 treatment the subject will be excluded from the study.

Subjects will be required to complete a patient diary to document the pain severity and pain relief before and after the administration of the study medication. In case the pain is not responding to the administered study drug after 30 minutes, subjects will be allowed to use only 100% oxygen or sumatriptan as a rescue management. If applicable and feasible, subjects in Period 1 may return to the study center for follow-up within 24 hour post treatment administration. The subjects will have a follow-up within 24 hours of the study drug administration in Period 2 where a PK sample will be collected, with a second PK sample collected to 1 to 2 hours after the 1st PK sample. In case the follow-up visit in Period 2 falls on a weekend, a window of up to 48 hours may be considered.

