### 3.2 Rationale for study design

Based on the nature of the studied disease and PK characteristics of SOM230, a single s.c. dose will provide an assessment of effect of SOM230 in managing cluster headache attack as well as the time to next attack. It is expected that a single dose of SOM230 will relieve the cluster headache attack and will delay the time to next attack resulting in reduced number of attacks per day. Given the nature of the disease (repeated attacks up to 8 attacks/day for up to 2 months), the relatively long half-life of SOM230, and to ensure consistency between attacks, treating 2 consecutive attacks in a one-sequence two-period design with a placebo treatment in Period 1 will be appropriate to cluster headache patients and will increase the statistical power by taking advantage of a within-patient comparison in the absence of carryover effects. The treatment effect will be confounded with the period effect in this one-sequence 2 period study. However, this is not a major concern considering the 2 periods are  $\leq 3$  days apart and we are looking for a substantial treatment effect. Subjects will be blinded to the sequence of treatment to minimize any potential bias. The Investigator input in this study will not have any influence on study outcome being solely entered by the subjects in the e-diary, thus the Investigators don't need to be blinded. Considering the severe pain associated with CH, patients benefiting from sumatriptan are expected to continue their conventional management that successfully relieves their pain. Accordingly, enrolled population in the study is expected to be mainly composed of non-sumatriptan users. To avoid confounding AE evaluation in

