## **11.1 Analysis sets**

For all analysis sets, subjects will be analyzed according to the study treatment received.

The safety analysis set will include all subjects that received any study drug.

The PK analysis set will include all subjects with available PK data and no protocol deviations with relevant impact on PK data.

The efficacy/PD analysis set will include all subjects that received any study drug and had no protocol deviations with relevant impact on efficacy/PD data.

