## 4 Statistical methods: Analysis sets

For all analysis sets, subjects will be analyzed according to the study treatment received.

The safety analysis set will include all subjects that received any study drug.

The PK analysis set will include all subjects with available PK data and no protocol deviations with relevant impact on PK data.

The efficacy/PD analysis set will include all subjects that received study drug in both periods and had no protocol deviations with relevant impact on efficacy/PD data.

The analysis sets and protocol deviation codes are related as follows:

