#### **6.1.3.3 Graphical presentation of results**

If there are sufficient data to analyze, then the time to headache response, time to pain free response and time to recurrence curves, using Kaplan-Meier estimates will be constructed by dose. A clustered log-rank test for correlated survival data will be performed to compare the time to event curves between treatments while hazard ratios will be estimated by the Cox proportional hazard frailty model with CH type and baseline headache severity or frequency included as covariates as appropriate. If subjects do not have an event, they will be censored at their last available visit. These analyses will only be conducted if the primary analysis indicates a significant result and if there is sufficient data.

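### Time to recurrence: an attack-free 72 hours drops out of the comparison after placebo but is kept as censored after SOM230, which tilts the curves towards an apparent delay if more than a handful of subjects are attack-free that long

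*SAP*

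**What the plan says.** - **Exclusion.** Both treated attacks follow a fixed order, placebo first. For a subject without an attack in the window after placebo, SAP 1.4 (and Protocol 3.1) states: "72 hours post Period 1 treatment the subject will be excluded from the study". Such a subject never receives SOM230.
- **Analysis set.** SAP 4: "The efficacy/PD analysis set will include all subjects that received study drug in both periods". Protocol 11.1 is wider: "The efficacy/PD analysis set will include all subjects that received any study drug and had no protocol deviations" with relevant impact on efficacy/PD data. SAP 6.1.3.3 does not say which set its curves use.
- **Endpoint and test.** SAP 6.1.3.3 plans that "time to recurrence curves, using Kaplan-Meier estimates will be constructed by dose". It continues: "A clustered log-rank test for correlated survival data will be performed to compare the time to event curves between treatments". Hazard ratios come from a Cox frailty model.
- **No event.** Same section: "If subjects do not have an event, they will be censored at their last available visit". After SOM230 the last visit is the end-of-study visit, 3 days after dosing.
- **Gate.** These analyses run only if the primary result is significant and the data are sufficient.
- **Expectation.** Protocol 3.2 expects that "a single dose of SOM230 will relieve the cluster headache attack and will delay the time to next attack". Protocol 3.3 gives a possibly longer interval to the next attack as one reason for the 1.5 mg dose.

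**The concern.** Under the SAP 4 set, a placebo record enters the recurrence comparison only if an attack followed within 72 hours. A SOM230 record has no such condition. The same outcome, three days without an attack, deletes the subject in Period 1 and counts in the drug's favour in Period 2. This is selection on the outcome in one period only.

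It is separate from the treatment-by-period confounding that Protocol 3.2 acknowledges, and no visible text addresses it. Under the current rule a frailty term or covariate cannot repair it, because the event-free placebo records are absent. At stake is a hazard ratio that would be reported exactly when the primary result looks promising, on an effect the protocol says it expects.

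**Working it through.** **The plan's own figures.** The documents give no event count, power or hazard ratio for time to recurrence, so there is nothing to reproduce. Cohort size comes from Protocol 11.6: 23 / (1 − 0.20) = 28.75, enrolled as about 30.

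**Structure.** Let q be the probability of no attack within 72 hours, the same in both periods (inert drug).
- Event-free at 72 hours, placebo records: 0% by construction.
- Event-free at 72 hours, SOM230 records: q, if the periods are independent.
- So the expected hazard ratio is below 1 whenever q > 0.

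**q at a constant attack rate r per day:** q = exp(−3r). The entry range of 2 to 6 a day is from Protocol 4.1.
- r = 2: exp(−6) = 0.25%
- r = 3: exp(−9) = 0.01%
- r = 4 to 6: below 0.001%
- r uniform on 2 to 6: (exp(−6) − exp(−18)) / 12 = 0.02%
- r = 1, below the entry average: exp(−3) = 5.0%

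**q when subjects differ** (gamma rates, mean m, shape a): q = (1 + 3m/a)^(−a).
- m = 3, a = 2: 5.5^(−2) = 3.3%
- m = 2, a = 1: 1/7 = 14.3%

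**Simulation, inert drug.** 30 subjects per cohort, 2,000 trials per scenario, Period 2 censored at 72 hours, marginal Cox hazard ratio, clustered log-rank. The SAP gives no level for this test; one-sided 0.05 is assumed. In the q rows a subject has no attack with probability q, independently in each period, at 3 attacks a day otherwise.

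| Scenario | HR, rule as written | False delay | HR, Period 1 record kept |
|---|---|---|---|
| Constant 2–6/day | 0.99–1.01 | 6–7% | no material change |
| q = 2% | 0.91–0.92 | 10–11% | 0.98 |
| q = 5% | 0.83 | 19% | 1.00 |
| q = 10% | 0.72–0.73 | 34% | 1.01 |
| Gamma, mean 3, shape 2 | 0.92–0.93 | 10% | 1.06 |
| Gamma, mean 2, shape 1 | 0.81 | 24–25% | 1.24 |

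With every subject observed in both periods, the hazard ratio is 0.99–1.01 and false delay 5–7%. A second simulation, at 2 to 4 attacks a day, gave 0.79–0.81 at q = 5% and 0.70–0.71 at q = 10% under the rule. Hence the rounded 0.8 and 0.7.

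**Subject-frailty model** (gamma frailty, exponential baseline, inert drug):
- Rates uniform on 2 to 6 a day: 0.99 under the rule.
- Gamma, mean 3, shape 2: 0.94 under the rule, 1.01 with the Period 1 record kept.
- Gamma, mean 2, shape 1: 0.79, then 0.99.
- q = 5%, bouts ending: 0.79, then 0.91.

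Keeping the record therefore helps, but the two models fail in different places. The marginal analysis over-corrects when attack rates differ between subjects. The frailty model handles that case but recovers only partly when bouts end.

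**The case against.** **What stands.**
- *Size.* Entry requires an average of 2 to 6 attacks a day. Subjects who keep to that almost never reach 72 attack-free hours. A reader might infer that the plan makes any inert drug look effective; the documents do not support that without a value of q.
- *Source of q.* A reader might take the 20% drop-out allowance in Protocol 11.6 as evidence. It is an unspecified allowance and is not linked to the 72-hour rule.
- *Definition.* No visible text defines recurrence, and parts of the exploratory sections are blacked out. A definition tied to a prior response, or a shorter window, would change the risk set.
- *Analysis set.* On its own wording Protocol 11.1 could keep a placebo-only subject. The point rests on SAP 4.
- *Reach.* The study is non-confirmatory and the analysis is gated. A reader might extend the point to the 30-minute primary result; this mechanism concerns time to recurrence. The attack-count analysis in Protocol 11.5.1 compares with baseline, not with the placebo period.

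**What does not remove the point.** The entry rate is an average. Chronic subjects are capped at 50% (Protocol 4), so at least half are episodic and a bout may end during the study. Writing a 72-hour rule shows that attack-free subjects were foreseen. The gate does not remove the bias; it means the biased figure appears only when the primary result is significant.

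**Conclusion.** The point holds in conditional form. Under SAP 1.4 with the SAP 4 efficacy set, an attack-free subject after placebo contributes nothing to time to recurrence, while one after SOM230 is kept as censored. The direction favours SOM230.

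The bias is negligible at steady rates of 2 to 6 attacks a day. It becomes material only if a few percent or more of subjects have no attack in 72 hours: a null hazard ratio of about 0.91 at q = 2%, 0.8 at 5% and 0.7 at 10%. All three values of q are assumptions.

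The conclusion also rests on reading recurrence as the next attack, which fits Protocol 3.2, and on the SAP's analysis set rather than the protocol's. A reader might infer that restoring the placebo record is a complete cure; the simulations do not support that. This is worth correcting before database lock, but it does not challenge the primary analysis.

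**What to change.** In SAP 6.1.3.3:
1. Define recurrence, with its time origin and risk set.
2. For this endpoint, use every subject dosed in the period concerned. This is consistent with Protocol 11.1; reconcile that section with SAP 4 in the same amendment.
3. Where no attack follows placebo, keep a Period 1 record censored at 72 hours, and apply the same 72-hour cut-off in Period 2.
4. Lead with the subject-frailty Cox hazard ratio, with attack frequency as covariate. Treat the marginal log-rank test as supportive, because it can over-correct when attack rates differ between subjects.
5. Report how many subjects the 72-hour rule removed. That count shows whether the bias matters in this trial.

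The cost is about one SAP paragraph. No study procedure or data collection changes. The downside is that some subjects contribute one record, residual bias in either direction is possible, and the apparent SOM230 delay may shrink.
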